2.2.2 Biomarkers to Predict Benefit from Treatment with Immune Checkpoint Inhibitors

Certain tumors are primed and ready to respond to treatment with an anti-PD-1 antibody, and others are not. Cancer patients who benefit from anti-PD-1 treatment are characterized as having “hot” tumors, whereas those who do not respond to anti-PD-1 treatment are characterized as having “cold” tumors. Several biomarkers have been proposed to classify a tumor as “hot” versus “cold,” including programmed cell death ligand-1 (PD-L1) expression, tumor mutation burden (Rizvi et al, 2015), interferon-gamma expression (Ayers et al, 2017), tumor immune signature (Chen et al, 2016), fecal microbiome profile (Gopalakrishnan et al, 2018), and the extent of the CD8 T-cell infiltrate (Hegde et al, 2016). These biomarkers have an association with the CD8 T-cell infiltrate (Maby et al, 2015; Thompson et al, 2017; Roy and Trinchieri, 2017). Several clinical studies have shown that clinical response to anti-PD-1 treatment is correlated with the pre-treatment number or the percentage of tumoral CD8 cells (Tumeh et al, 2014; Chen et al, 2016; Johnson et al, 2016). Therefore, larger numbers of tumoral CD8 cells may be a useful biomarker to identify “hot” (CD8 high) tumors.

Furthermore, an increase in tumoral CD8 cells has been observed after anti-PD-1 treatment, and this increase is associated with improved clinical outcomes in melanoma and squamous cell carcinoma of the head and neck (SCCHN; Chen et al, 2016; Concha-Benavente et al, 2017). Following anti-PD-1 treatment, a significant increase in intratumoral CD8 cells was seen in responders but not in non-responders (Figure 5).

[figure not shown]
Figure 5: Tumor-infiltrating CD8 T-cell Expression in Responders and Non-responders to PD-1 Blockade

Tumor samples were stained by immunohistochemistry with pooled data in panel A and representative images in panel B. Adapted from [Chen et al. 2016](#).

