9.4.1 Efficacy Analyses

The efficacy analysis will be based on the modified Intent-to-Treat (mITT) Population, which comprises all enrolled participants with sufficient biopsy results to be assigned to a treatment arm and who received at least one dose of study drug, unless otherwise specified. Participants will be analyzed according to the study intervention to which they were assigned.

The primary endpoint of CBR will be reported among all participants within each study intervention group with a 95% credible interval assuming a beta (0.4, 1.6) prior. Per RECIST, to

be assigned a best overall response of CR or PR, changes in tumor measurements must be confirmed by a repeat assessment that should be performed no less than 4 weeks after the criteria for response are first met. Participants who do not have a disease assessment will be counted as not having clinical benefit. In addition, CBR and similar credible intervals will be reported for each tumor site and study intervention subgroup that has at least 10 participants.

The proportion of participants whose tumors change from CD8 low to CD8 high expression will be reported with a 95% credible interval with no prior as this is the first look.

For secondary endpoints, baseline CD8 counts will be explored for association with CBR using logistic regression models and with OS using Cox regression models. Multivariate models will be explored with up to 1 variable for every 10 events. For CBR prediction, an event is an objective response (CR or PR or SD as defined above). For association with survival, an event is a participant death.

Among the On-treatment Biopsy Population, both the baseline and on-treatment biopsies will be associated with response and survival using similar logistic and Cox regression models described above, assuming there are sufficient events to carry out the regression analyses. The association of CD8 changes from baseline to on treatment with clinical outcomes will also be explored.

The exploratory endpoint of changes in PSA (absolute and percent) from baseline will be analyzed by cohort for advanced prostate cancer participants.

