**Table 2: Populations for Analysis**

| Population                                 | Description                                                                                                                                                                                                                      |
|--------------------------------------------|----------------------------------------------------------------------------------------------------------------------------------------------------------------------------------------------------------------------------------|
| Safety Population                          | All participants who received at least one dose of study drug. Participants will be analyzed according to the study intervention actually received.                                                                              |
| Modified Intent-to-Treat (mITT) Population | All participants with sufficient biopsy results to be assigned to a treatment arm and who received at least 1 dose of study drug. Participants will be analyzed according to the study intervention to which they were assigned. |
| On-treatment Biopsy Population             | All participants with at least 1 on-treatment biopsy with sufficient CD8 results will be included in the analyses of changes in CD8 counts.                                                                                      |

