#### 5.4.2.4 Association of CD8 with clinical outcomes

Several analyses will be performed to investigate the association between the percentage of CD8 cells and clinical outcomes.

- Among the participants who had tumors that converted from cold (CD8 <15%) at baseline to hot (CD8  $\geq$  15%) at any on-treatment biopsy, the following will be reported:
  - The number and proportion of patients who met ORR response criteria. A 95% credible interval will be estimated with no prior.
  - The number and proportion of patients who met CBR response criteria. A 95% credible interval will be estimated with no prior.
- Logistic regression models will be fit to assess the relationship between percentage of CD8 and clinical response (ORR and CBR). Each regression model will include an intercept term. P-values will be calculated using a Wald test to test whether the coefficient for the CD8 variable is significantly different from 0. See Table 3 for details about each regression model.

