**Table 3: Logistic Regression Model Parameters**

| Model number | Response variable (y) | Explanatory variable (x)                                                                              | Analysis Population            |
|--------------|-----------------------|-------------------------------------------------------------------------------------------------------|--------------------------------|
| 1            | CBR                   | Baseline percentage of CD8 cells                                                                      | mITT Population                |
| 2            | ORR                   | Baseline percentage of CD8 cells                                                                      | mITT Population                |
| 3            | CBR                   | Maximum percentage of CD8 cells across all on-treatment biopsies                                      | On-treatment Biopsy Population |
| 4            | ORR                   | Maximum percentage of CD8 calls across all on-treatment biopsies                                      | On-treatment Biopsy Population |
| 5            | CBR                   | Absolute change between baseline and maximum percentage of CD8 cells across all on-treatment biopsies | On-treatment Biopsy Population |
| 6            | ORR                   | Absolute change between baseline and maximum percentage of CD8 cells across all on-treatment biopsies | On-treatment Biopsy Population |
| 7            | CBR                   | CD8 Conversion Flag
(1 = CD8 converter, 0 = non-converter)                                         | On-treatment Biopsy Population |
| 8            | ORR                   | CD8 Conversion Flag
(1 = CD8 converter, 0 = non-converter)                                         | On-treatment Biopsy Population |

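### SAP Table 3 Models 5-8 leave out baseline CD8, so their Wald tests cannot separate an on-treatment CD8 change from where the tumor started

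*SAP*

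**What the plan says.** SAP 5.4.2.4 lists eight logistic models in Table 3. On their form it says only "Each regression model will include an intercept term", and each row names one explanatory variable. Models 5 (CBR) and 6 (ORR) use "Absolute change between baseline and maximum percentage of CD8 cells across all on-treatment biopsies". Models 7 (CBR) and 8 (ORR) use a flag coded "1 = CD8 converter, 0 = non-converter". Inference is by p-value: "P-values will be calculated using a Wald test to test whether the coefficient for the CD8 variable is significantly different from 0".

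All four models are assigned to the On-treatment Biopsy Population, defined in SAP Table 2: "All participants with at least 1 on-treatment biopsy with sufficient CD8 results will be included in the analyses of changes in CD8 counts". That includes the CD8-high arm, which is also biopsied on treatment (Protocol 4.1). SAP 5.4.1 defines a converter as a participant below 15% at baseline who reaches at least 15% on any on-treatment biopsy, so CD8-high participants cannot convert. The SAP does not say whether Models 7-8 exclude them or code them 0.

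Protocol 9.4.1 is broader: "The association of CD8 changes from baseline to on treatment with clinical outcomes will also be explored", and "Multivariate models will be explored with up to 1 variable for every 10 events". The SAP takes precedence over the protocol and lists no model with more than one variable.

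**The concern.** Conversion means crossing a fixed line from below. A tumor at 14% needs 15 - 14 = 1 point; a tumor at 1% needs 15 - 1 = 14. Change is a difference from baseline, so it too is tied to baseline. Protocol 2.2.2 reports that "clinical response to anti-PD-1 treatment is correlated with the pre-treatment number or the percentage of tumoral CD8 cells", and Models 1-2 test that relation. Baseline is therefore a confounder that the sponsor expects and measures.

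The null tested by Models 5-8 is no marginal relation between change (or conversion) and response. It can fail when baseline alone matters. CD8 conversion is a primary objective, and the rationale is that the combination turns low tumors into high ones. A small p-value in Model 7 would be read as support for that mechanism. As specified, it could equally mean that tumors starting near 15% do better.

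**Working it through.** **Inputs from the documents (Protocol 9.1).** 200 participants, about 40 CD8-high and 160 CD8-low; CBR 20%; illustrative conversion rates of 10% and 50%. The protocol's interval for 32/160 with a beta(0.4, 1.6) prior reproduces: the posterior is Beta(32.4, 129.6), with 95% limits 14.2% and 26.5%, as stated. The documents give no power, alpha or error rate for Models 1-8, so two-sided 0.05 is assumed below.

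**Inputs not in the documents.** Main set: log-normal CD8 with 20% of tumors at or above 15% and log-SD 0.9; one on-treatment biopsy; correlation of repeat biopsies 0.7-0.9; average fold change 1.0-2.0 with between-participant log-SD 0.4, unrelated to response. Conversion then comes out at 14-36%. Response is drawn from logit(p) = a + log(OR) x standardised baseline CD8, with a set so that CBR is 20%. The SD is that of the CD8-low group. With 1,500 trials per cell, the simulation error at 5% is sqrt(0.05 x 0.95 / 1500) = 0.6 percentage points.

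**CD8-low only, n=160, baseline-only effect: share of trials with Wald p < 0.05.**

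| Scale of baseline effect | OR per SD | Model 7 | Model 5 | Either, baseline added |
|---|---|---|---|---|
| raw CD8% | 1.5 | 12-23% | 6-12% | 3-5% |
| raw CD8% | 2.0 | 20-52% | 8-27% | 3-5% |
| log CD8 | 1.5 | 10-20% | 6-12% | 3-5% |
| log CD8 | 2.0 | 17-40% | 7-20% | 3-5% |

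The conversion odds ratio produced by baseline alone is about 1.4-2.3 (raw) or 1.35-2.0 (log). At n=110 on the raw scale, Model 7 rejects in 9-16% (OR 1.5) and 15-38% (OR 2.0). With no baseline effect, rejection is about 2-6%.

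**Whole On-treatment Biopsy Population, N=200, CD8-high coded 0, same assumptions.** Model 7 rejects in favour of conversion in 0.3-2.8% (raw) or 1-7% (log), against a nominal 2.5%. The odds ratio is about 1 on the log scale, and rejections against conversion reach 9% on the raw scale. Participants who cannot convert, and who respond more often because their baseline is high, fill the non-converter group. Model 5 rejects in about 7-37%.

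**Wider set.** Log-SD 1, maximum of two on-treatment biopsies, correlation 0.3-0.8, OR 1.5-3, conversion fixed at 10% or 50%.
- Pooled Model 5 rejects in 7-98%, with either sign: on the raw scale at OR 2, 88.6% negative (correlation 0.3, 10% conversion) and 30.9% positive (correlation 0.8, 50% conversion).
- Pooled Model 7 rejects in favour of conversion in 0-6% and against it in up to 44%.
- CD8-low Model 7 rejects in favour of conversion in 3-61%. At OR 2 and correlation 0.8 it is 16-33% on the log scale, but total rejection on the raw scale is only 6.9% and 8.6%. The low raw-scale figures are what one expects if the SD is taken over all tumors, because the range below 15% then spans little of it.

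**If response follows the tumor's underlying CD8 rather than the biopsy reading.** Baseline-adjusted rejection in CD8-low participants is about 5-14% for Model 7 and 6-17% for Model 5, and up to about 20% across the runs. The second biopsy corrects error in the first, so it carries information even when treatment-induced change carries none.

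**Events available.** 0.20 x 160 = 32 CBR events; 32 / 10 = 3.2, so three variables are allowed. The adjusted model needs two, hence 20 events, hence 20 / 0.20 = 100 CD8-low participants with an on-treatment result.

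**The case against.** The strongest reply is that SAP 5.4.2.4 promises only association, and SAP 5.4 disclaims hypothesis testing and type I error control. That stands: no alpha is stated, so none is breached. But lack of error control does not deal with confounding, and p-values are still specified.

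Four stronger readings are tempting, and the documents do not support them.
- A reader might infer that the plan will credit conversion with an effect. That requires Models 7-8 to be limited to CD8-low participants, which Table 3 does not say. SAP 5 presents summaries by intervention group, so a within-arm fit is possible, but it is not specified. In the population Table 3 names, Model 7 is near null or negative.
- A reader might infer that the association does not exist. The marginal association is real; only its independence from baseline is unsupported.
- A reader might treat the rejection rates as properties of this trial. The baseline odds ratio, correlation, log-SD and fold change are all assumed, and some settings stay near 5%. The protocol's premise concerns anti-PD-1 treatment in general and gives no gradient below 15% under the combination.
- A reader might infer that adjustment restores 5%. That holds only if response follows the measured baseline reading.

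**Conclusion.** The point holds as one of bias and interpretation. Models 5-8 cannot distinguish an on-treatment CD8 change from baseline CD8. If baseline alone predicts response, Model 7 in CD8-low participants rejects in favour of conversion in roughly 10-50% of trials over the main settings. With CD8-high participants pooled and coded 0, Model 7 hides the problem and Model 5 can err in either direction. The sizes rest on the assumed inputs above; the structural fault does not. Models 6 and 8 have the same form but were not simulated. The SAP should be changed, because the remedy is cheap and the result bears on the trial's main hypothesis.

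**What to change.** In SAP Table 3:

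1. Restrict Models 7-8 to participants with baseline CD8 below 15%.
2. Add baseline percentage of CD8 cells as a covariate to Models 5-8, and take the odds ratio and Wald test for change or conversion from that model. Keep the unadjusted fit as a descriptive line.
3. Where there are fewer than 20 events, report only the unadjusted fit and make no claim about conversion. This is likely for ORR, whose events are a subset of CBR events. It is possible for CBR too, since on-treatment biopsies depend on medical feasibility.
4. Show the baseline CD8 distribution for converters and non-converters beside the CBR and ORR reported among converters.
5. State that adjustment reduces but does not fully remove confounding, because baseline CD8 is measured with biopsy error; adjusted rejection may still be about 5-20%.

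The cost is a table edit and one covariate that enrollment already requires. The downside is one extra parameter in models with few events.

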**Table 3: Logistic Regression Model Parameters**

| Model number | Response variable (y) | Explanatory variable (x)                                                                              | Analysis Population            |
|--------------|-----------------------|-------------------------------------------------------------------------------------------------------|--------------------------------|
| 1            | CBR                   | Baseline percentage of CD8 cells                                                                      | mITT Population                |
| 2            | ORR                   | Baseline percentage of CD8 cells                                                                      | mITT Population                |
| 3            | CBR                   | Maximum percentage of CD8 cells across all on-treatment biopsies                                      | On-treatment Biopsy Population |
| 4            | ORR                   | Maximum percentage of CD8 calls across all on-treatment biopsies                                      | On-treatment Biopsy Population |
| 5            | CBR                   | Absolute change between baseline and maximum percentage of CD8 cells across all on-treatment biopsies | On-treatment Biopsy Population |
| 6            | ORR                   | Absolute change between baseline and maximum percentage of CD8 cells across all on-treatment biopsies | On-treatment Biopsy Population |
| 7            | CBR                   | CD8 Conversion Flag
(1 = CD8 converter, 0 = non-converter)                                         | On-treatment Biopsy Population |
| 8            | ORR                   | CD8 Conversion Flag
(1 = CD8 converter, 0 = non-converter)                                         | On-treatment Biopsy Population |

